The screening of subjects using the inclusion and exclusion criteria, and the comprehensive medical and psychiatric evaluation will minimize the risk of including subjects who are otherwise inappropriate. Confidentiality in regard to collected materials will be maintained via a numbered reference system maintained by the Project Coordinator. Subjects' names will appear only on a consent form and "key" form kept by the PI and the Project Coordinator in a separate location.

- b. How will the research data be collected, recorded and stored?
- c. How will the digital data be stored? CD DVD Flash Drive Portable Hard Drive Secured Server Laptop Computer Desktop Computer Other
- d. What methods and procedures will be used to safeguard the confidentiality and security of the identifiable study data and the storage media indicated above during and after the subject's participation in the study?

Upon enrollment, all study subjects will be assigned a unique study number. The study number—and no personal identifiers—will be used as labels for study records, samples and any other related research documentation. All electronic and digital files will be stored on the secure Yale network, and the PC accessing the network will be password protected and encrypted. All paper files, such as consent forms, will be stored in a locked file cabinet in a locked office and access is limited to members of the study research team.

Do all portable devices contain encryption software? Yes No NA as per above
If no, see <http://hipaa.yale.edu/guidance/policy.html>

- e. What will be done with the data when the research is completed? Are there plans to destroy the identifiable data? If yes, describe how, by whom and when identifiers will be destroyed. If no, describe how the data and/or identifiers will be secured.

Upon completion of study and data analysis, a professional information protection, storage, and disposal company will be retained to dispose of research files and informed consent documentation.

f. Who will have access to the protected health information (such as the research sponsor, the investigator, the research staff, all research monitors, FDA, Yale Cancer Center Data and Safety Monitoring Committee (DSMC), SSC, etc.)? (please distinguish between PHI and de-identified data)

All de-identified data will be available to the research investigator PI, Co-Investigator, statistician, DSM, research staff responsible for entering data, NIH/NIAAA, Yale HRRP, and Yale's HIC. Protected Health Information will be available to the research physician, and research staff only when deemed necessary.

g. If appropriate, has a [Certificate of Confidentiality](#) been obtained?

A Certificate of Confidentiality has been obtained from the National Institutes of Health.

h. Are any of the study procedures likely to yield information subject to mandatory reporting requirements? (e.g. HIV testing – reporting of communicable diseases; parent interview -incidents of child abuse, elderly abuse, etc.). Please verify to whom such instances will need to be reported.

Mandatory reporting of incidents of abuse or neglect of a child or elderly person as required by Connecticut State law will be complied with. Additionally, certain reportable infectious diseases such as HIV and Hepatitis B and C will be reported to the appropriate state agency, although these will not be tested by the study. We may also need to intervene and report information regarding threat of injury to self or others to the proper authorities. All of these requirements will be complied with.

SECTION IX: POTENTIAL BENEFITS

Potential Benefits: Identify any benefits that may be reasonably expected to result from the research, either to the subject(s) or to society at large. (Payment of subjects is not considered a benefit in this context of the risk benefit assessment.)

The proposed study has the potential to reveal novel mechanisms that may play a role in alcohol addiction. A better understanding of alcohol use disorder is of utmost importance in order to develop improved treatments for alcohol use disorders. Understanding the potential role of neuroactive steroids in alcohol addiction could also aid in our knowledge of the role of sex hormones and their precursors and derivatives in this disorder, and thereby allow us to potentially address gender differences that exist in the development, progression and relapse of alcohol use disorder.

SECTION X: RESEARCH ALTERNATIVES AND ECONOMIC CONSIDERATIONS**1. Alternatives:** What other alternatives are available to the study subjects outside of the research?

Subjects need not participate in this study to receive treatment for alcohol use disorder, such as approved pharmacotherapies and counseling, group therapy, and psychotherapy.

2. Payments for Participation (Economic Considerations): Describe any payments that will be made to subjects, the amount and schedule of payments, and the conditions for receiving this compensation.

Subjects completing the Study will receive \$20 for a remote intake interview session or \$25 for an in-person intake interview session, \$25 for the imagery and relaxation training session, and \$100 for each of the 3 laboratory sessions. Subjects will also be paid a \$50 bonus for completing the laboratory sessions. Therefore, for the completion of all procedures leading up to and including the laboratory sessions, subjects will receive up to a total of \$400.

If subjects continue on to complete the treatment phase, they will earn chances to win dollar prizes for kept appointments to encourage appointment attendance. For every twice/weekly appointments they attend, the chance to draw a prize from the fishbowl will increase by one. The fishbowl prizes are in increments of \$1, \$5, \$20, and \$100. Subjects will participate in this at every twice/weekly appointment they attend. If they miss any appointment, or fail to take study medication, the chances will be reset back to one. For example, if no appointments are missed the subject will have a total of 8 chances at the last appointment. Each prize increment that is won from the 8 attempts is then added together into a lump sum. There is no limit on the amounts that can be won. A standard payment rate of \$20 per week can be used in lieu of drawing from the fish bowl in order to encourage completion of appointments.

Subjects participating in smartphone monitoring will be compensated for their participation at \$2 a day, with a \$6 bonus for completing all 7 days, hence a possible total of \$20 a week, or \$160 for all 8 weeks of the study. Subjects will receive \$25 per week for taking study medication using eMocha for a total of \$200 for completing all 8 weeks. In addition, subjects will receive \$25 for week 3, \$25 for week 5, \$25 for week 7, and a \$25 bonus for completing the treatment phase. The total that subjects may be reimbursed if they complete all aspects of the study will be \$860 plus the various amounts won for keeping appointments during the treatment phase.

If a subject decides to not continue with the treatment phase, twice-weekly follow-up appointments for one week will be scheduled after the laboratory sessions are complete. They will receive \$25 for each visit. Therefore, if subjects only complete the laboratory phase with the follow up visits and smartphone monitoring, the maximum total payment will be \$490.

3. Costs for Participation (Economic Considerations): Clearly describe the subject's costs associated with participation in the research, and the interventions or procedures of the study that will be provided at no cost to subjects.

There will be no costs charged to subjects who participate in this study. All evaluations including interviews, physical exams, diagnostic tests will be provided at no cost to the subjects.

4. **In Case of Injury:** This section is required for any research involving more than minimal risk.

- a. Will medical treatment be available if research-related injury occurs?
- b. Where and from whom may treatment be obtained?
- c. Are there any limits to the treatment being provided?
- d. Who will pay for this treatment?
- e. How will the medical treatment be accessed by subjects?

While medical therapy will be offered for any physical injuries sustained as a consequence of participation in this research, the subject and their insurance carrier will be responsible for the cost of such treatment. Financial compensation for injury is not available.

REFERENCES

Beck, A., C. Ward, et al., (1961). "An inventory for measuring depression." *Archives of General Psychiatry* 4: 461-471.

Bradley, B. P., Phillips, G., Green, L., Gossop, M., (1989). "Circumstances surrounding the initial lapse to opiate use following detoxification." *Br. J. Psychiatry.* 154, 354-359.

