3. **Research Plan:** Summarize the study design and research procedures using non-technical language that can be readily understood by someone outside the discipline. **Be sure to distinguish between standard of care vs. research procedures when applicable, and include any flowcharts of visits specifying their individual times and lengths.** Describe the setting in which the research will take place.

1. Study Design and Overview

Ninety treatment seeking men and women with AUD will be recruited to participate in and complete this preliminary study. Participants will be recruited through flyers and advertisements in local newspapers and from community substance abuse treatment facilities. Subjects will participate in an initial screening and intake session to obtain informed consent, followed by physical examination and blood work to determine eligibility. Eligible

participants will be randomly assigned to 2 doses of PREG (300/500 mg/day) vs placebo (PLA) treatment (N=30/group) over 8 weeks. In week 2, AUD patients will participate in a 3day human laboratory study where they will be exposed to three experimental sessions of stress, alcohol cue and neutral-relaxing imagery on separate days (Fox et al.,2007; 2009; Sinha et al., 2008; 2009; 2011). Throughout the study, participants will come twice-weekly to the Yale Stress Center to receive medication, counseling and provide urine samples for UTOX. Women will be enrolled during the mid-luteal phase of the menstrual cycle so that laboratory sessions will be scheduled during the early to mid-follicular phase of the cycle when endogenous sex hormone levels are low prior to ovulation. PREG doses and matching placebo will be obtained by Yale IDS for compounding and dosing to 300mg and 500mg of PREG or PLA. Participants will self-administer study medication on a twice-daily dosing schedule throughout entire study.

Subjects will begin with full respective dose of medication immediately without a titration period, as previous studies with similar doses of pregnenolone up to 500 mg/day at b.i.d. dosing to be well tolerated and with no side effects (Marx et. al., 2009; Marx et al., 2014; Brown et al., 2014; Sripada et al., 2013).

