The *Structured Clinical Interview for DSM-V (SCID, First et al., 1995)* will be used to obtain DSM-V alcohol and other substance use disorder diagnoses. The SCID's reliability and validity among substance-using populations has been established in large-scale surveys (Kranzler et al., 1996). The number of dependence syndrome elements endorsed from the DSM-V substance abuse/dependence criteria will assess severity of alcohol and other drug use disorder. The SCID will also be used to obtain previous psychiatric diagnoses.

Medical History and Physical Examination: All patients will be required to participate in a physical examination including a medical history, electrocardiogram (EKG), blood, and urine laboratory assessments prior to initiation of PREG/PLA to ensure eligibility for pregnenolone study protocol. Female patients will also have a pregnancy test. These tests will be conducted at the Yale Stress Center under [name] supervision. Subjects will also have the option to visit a Quest Diagnostics location to provide blood and urine specimens.

The California Psychological Inventory (CPI-So) (Gough, 1951) is the socialization scale of the CPI personality test used to assess the degree of social maturity, integrity, and rectitude that the individual has attained.

The Patient-Reported Outcomes Measurement Information System (PROMIS) 29 Profile is a NIH developed patient reported outcome measurement tool that measures physical functioning, anxiety, depression, fatigue, sleep disturbance, social role participation and pain, that have a major impact on quality-of-life across a variety of chronic diseases.

Substance Use: Alcohol and Drug Use Measures:

The Alcohol Urge Questionnaire (AUQ) is a brief 8-item self-report craving scale used to measure alcohol craving. The AUQ will be given weekly and at follow-up interviews.

The Addiction Severity Index (ASI: McLellan et al., 1992) is a structured interview that assesses the severity of substance use and substance-related problems in the areas of medical, employment, legal, family/social and psychiatric functioning. The ASI is the most widely used instrument for assessment of substance use and related problems and its psychometric properties are well-established (Cacciola et al., 1997). The ASI will be used at pre-treatment and week 8. Follow-up ASI interviews will be conducted at 30 days post-treatment.

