The Substance Use Calendar was developed by Miller and DelBoca (1994) and is based on the Time-Line Follow-Back Method (TLFB) (Sobell, Maisto et al. 1980). The SUC uses a calendar prompt and a number of other memory aids (e.g., holiday, payday, and other personally relevant dates) to facilitate accurate recall of daily drug use during the targeted period. It has demonstrated adequate levels of reliability and validity when administered as an in-person interview, over the telephone, and when administered via computer (e.g. Carey, 1997; Sobell, Brown, Leo, & Sobell, 1996; Sobell, Sobell, Leo & Cancilla, 1988). Its reliability and validity in drug abusing samples has also been established (Fals-Stewart, et al., 2000). In the current study we will use to obtain self-report of day to day use of alcohol, and other drugs, for the 90 days prior to treatment and weekly during treatment.

The Smoking History Questionnaire will be given to collect information on current and past smoking habits. The questionnaire also questions the subject's number of past quit attempts, their perception of health risks, and perceived barriers to quitting.

Fagerstrom Test for Nicotine Dependence (FTND: Fagerstrom, 1978) is a 6-item questionnaire for assessing tobacco dependence, which evaluates, among other factors, depth of inhalation, time from awakening to day's first cigarette, and difficulty in smoking cessation.

The Alcohol Use Disorders Identification Test (AUDIT) (Bohn et al., 1995) is a 10-item screening tool developed by the World Health Organization (WHO) to assess alcohol consumption, drinking behaviors, and alcohol-related problems.

Alcohol Dependence Scale (ADS) is a 25 item to measure severity of alcohol dependence.

Abstinence Measures:

Clinical Institute Withdrawal Assessment (CIWA) is a 13 item scale that measures alcohol withdrawal signs and symptoms. The assessment will be administered weekly and at followup interviews.

Cocaine Selective Severity Assessment (CSSA) is an 18-item scale that measures the cocaine withdrawal signs and symptoms within the past 24 hours. The CSSA will be used weekly and at the follow-up interview.

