Urine Toxicology and Breathalyzer Screening: A urine toxicology screen will be conducted at intake to confirm alcohol, and nicotine use. During treatment, urines will be collected 2 times weekly to confirm sobriety. In addition, urine samples will be taken weekly during treatment and at follow-up appointment using on-site TESTCUP5 Drug Screen (Roche Diagnostics Inc., Totowa, NJ) to monitor opiate and other drug use. The TestCup5 kit provides results for opioids, cocaine, THC, PCP and barbiturates. Continine levels in the urine will also be measured. Breath alcohol levels will also be assessed with the Alcosensor III Intoximeter, and carbon monoxide levels with a carbon monoxide breathalyzer, at each face-to-face contact, 2 times weekly.

Alcohol Urge Questionnaire (AUQ) is an 8-item self-report questionnaire that measures current craving state. This self-report will be completed weekly throughout the study.

Cocaine Craving Questionnaire (CCQ) is a 10-item self-report questionnaire that measures current craving state. This self-report will be completed weekly throughout the study.

The Treatment Review Scale (TRS), an adapted version of the Treatment Services Review (TSR) (McLellan, Kushner et al. 1992) will be administered weekly during treatment to assess participation in self-help. *The Questionnaire on Smoking Urges (QSU (brief))* is a 10item self-report measure designed to assess urges and cravings to smoke, with higher scores indicating stronger urges. Subjects will complete the questionnaire weekly and at follow-up interviews.

Thought About Abstinence Scale (TAAS) (Hall et al, 1990) is a four-item scale used to assess motivation to quit and abstinence self-efficacy.

Assessment of Psychological Symptoms:

A number of self- report measures of psychological functioning will be obtained weekly to examine pregnenolone's effects on psychological functioning. The following well-established and reliable instruments will be used:

The Emotion Regulation Scale (ERS) (DERS) is a 36-item questionnaire to provide a comprehensive measure of the difficulties in emotion regulation.

The Hospital Anxiety and Depression Scale (HADS; Zigmond and Snaith, 1983) is a 7 item, brief measure of generalized symptoms of anxiety and fear. Respondents indicate how they currently feel and responses are rated on a 4-point Likert scale and range from 0 to 3.

Obsessive Compulsive Disorder Scale (OCDS) is a 14 item test to measure obsessionality and compulsion.

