The Barratt Impulsiveness Scale, Version 11 (BIS-11; Patton et al., 1995) is a 30 item self-report questionnaire designed to assess general impulsiveness. The structure of the instrument allows for the assessment of six first-order factors (attention, motor, self-control, cognitive complexity, perseverance, cognitive instability) and three second-order factors (attentional impulsiveness [attention and cognitive instability], motor impulsiveness [motor and perseverance], nonplanning impulsiveness [self-control and cognitive complexity]).

The Life Orientation Test (LOT-R) (Scheier and Carver (1985) is a scale containing eight items that measures an individual's level of optimism.

The Brief Self-Control Survey (SCS) (Tangney et al., 2004) measures an individual's perceived ability to exercise his/her self-control in a variety of domains, including selfdiscipline, deliberate/nonimpulsive action, healthy habits, work ethic, and reliability.

Stress-Related Assessments:

The Chronic Stress Checklist is adapted from Turner's (1995) widely used Checklist Measures of Stressful Life Events. It will be used to assess for both chronic and recent life stress.

Perceived Stress Scale (PSS; Cohen et al., 1983) assesses the degree to which situations are appraised as threatening or otherwise demanding and that there are insufficient resources to cope with the situation. This global measure of perceived stress has been widely used in the behavioral medicine literature to examine the effects of stress on disease and treatment outcome. The PSS is a 14 item self-report measure with adequate reliability and both predictive and construct validity. It has been shown to predict smoking reduction in a smoking cessation treatment program (Cohen et al., 1983; Cohen & Lichtenstein, 1990). It will be used to assess stress levels weekly in study patients during treatment and at the follow-up appointment (copy included in Appendix B).

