The COPE Questionnaire (Carver, Scheier et al. 1989) is a multidimensional coping inventory that assesses the different ways in which people respond to stress. It is a 53-item self-report measure that assesses 14 coping strategies categorized into three coping styles (Problem Focused Coping; Emotion Focused Coping; Less-Useful Coping). While most previously developed coping scales have lacked good empirical validation, the COPE questionnaire has been developed with good overall reliability and construct validity, and is judged as an adequate measure of coping strategies (Parker & Endler, 1992). In this study we will assess stress-related coping at baseline and once during treatment and at the follow-up to assess effects of study medication on stress-related coping.

Cognitive assessments

CANTAB (Cambridge Cognition, Inc) Battery will be administered at baseline (first week of study enrollment) and again at some point during pregnenolone treatment. All CANTAB tasks incorporate testing modes suitable for use across multiple time-points and are presented on a touch-screen computer.

Stroop Color Word Test (Golden, 1976). On the initial trial participants are given 45 seconds to read as quickly as possible a list of 100 color words (red, green, blue) randomly arranged and printed in black ink. On the second trial participants have 45 seconds to identify as quickly as possible the color of 100 "XXXX" printed in either red, green or blue ink. The final trial consists of the 100 words presented in the initial trial in the colors presented in the second trial. In all cases, the word (i.e. red) is different from the color it is printed in (i.e. blue. (e.g. "red"). Subjects are given 45 seconds to name the color of the ink as quickly as possible. The number of raw items read for each trial is recorded and converted to standardized T scores. (5 mins)

Safety and Side Effects Measures

The following safety measures will be assessed at each contact with the patient:

Sitting vital signs: including heart rate, systolic and diastolic blood pressure will be assessed every 15-30 minutes for one hour 2x weekly throughout study. Laboratory chemistry will be assessed at week 2, 5 and week 7 after initial assessment for abnormal values.

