Reporting of Other Study-Safety Events: The project PI will inform the Data Safety Monitor, the Yale HIC, NIDA project officer and the sponsor promptly of any change in recruitment or other changes in this project that are relevant to safety, as well as any action taken by the Yale HIC as a result of continuing review of this project.

12. Statistical Considerations: Describe the statistical analyses that support the study design. For this preliminary study data we will mostly use descriptive statistics for comparing the medication groups on primary outcome measures and safety measures. Repeated measures ANOVA and mixed model procedures to assess treatment group differences in alcohol craving and stress related arousal (heart rate, blood pressure, HPA and catecholamine responses) during laboratory exposure to stress and drug cues as compared to neutral imagery conditions. Non-parametric tests will be used to assess occurrence of side effects, alcohol use measures, CIWA scores and perceived stress scores during the treatment study phase. The number and type of AE's for the two medication groups will be conducted using t-tests, chisquare tests and ANOVAs as appropriate. Findings will be used to estimate effect sizes for the medication and guide the larger randomized clinical trial in the future.

Primary Outcome Measures during 8 week treatment: The primary outcome measures will be:(1) alcohol use as measured by weekly urine drug screens and self-report of drug use on the Substance Use Calendar, (2) side effects and adverse events as measured by the SAFTEE, and (3) treatment adherence as measured by frequency of attendance for medication selfadministration and attendance for counseling appointments, including missed sessions.

Secondary Outcome Measures: Secondary outcome measures will include alcohol craving scales, alcohol withdrawal assessment using the CIWA, perceived stress scale, the recent stressful life events scale (LES), and the COPE Questionnaire. In addition, other assessments will be used to ensure that medications groups are not different in various measures at baseline and also to assess their role in predicting treatment response. Examples of such

assessments would be demographic measures, depressive and anxiety symptoms, motivation to change and thoughts about abstinence, which are measures that have been found to predict substance abuse treatment outcomes (Hall et al., 1990; 1991; McMahon et al., 1986).

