We selected 300mg and 500 mg/day versus placebo dosing based on prior clinical trials of pregnenolone in psychiatric patients (men and women). In an 8-week clinical trial in schizophrenia patients, fixed escalating dosing from 100mg to 500mg of pregnenolone (Marx et al., 2009) was well tolerated. The only side effects present in the pregnenolone group to a greater degree than the placebo group were two reports of mild restlessness, one report of mild muscle pain/stiffness, and one report of mild cold extremities. A follow-up randomized clinical trial in men and women with schizophrenia used escalating doses of pregnenolone, 100mg for 2 weeks, 300mg for 2 weeks, 500mg for 4 weeks, and found pregnenolone to be safe and well tolerated (Marx et al., 2014). A 12-week randomized placebo-controlled trial of escalating doses of pregnenolone to 400mg daily for 4 weeks in men and women with bipolar depression improved depressive symptoms and showed pregnenolone to be safe and well tolerated in all patients (Brown et al., 2014). A recent study using an acute dose of pregnenolone of 400mg to examine the effects of ALLO its effects on emotion regulation neurocircuitry (Sripada et al., 2013), also didn't find any side effects.

3. Source: a) Identify the source of the drug or biologic to be used.

Medication Administration and Compliance: Pregnenolone and matching placebo pills will be provided by Yale IDS Pharmacy who will make up identical active and placebo capsules, packaged into weekly packs for medication self-administration. Subjects will be randomly assigned to twice daily dosing of 300mg and 500mg PREG/PLA. Subjects will selfadminister study medication twice daily. Study staff will monitor vital signs and side effects during bi-weekly face-to-face appointments. We expect all subjects to tolerate doses of 300mg and 500mg pregnenolone. Alcohol craving, abstinence symptoms, mood and perceived stress scale and side effects will be assessed twice weekly. Urines will be obtained twice weekly.

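### No pre-dose AUQ, CIWA or PSS is specified, and the planned analysis would not reliably use one, so these secondary comparisons may be less precise than they could be

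*Combined protocol and SAP*

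**What the plan says.** Section V.12 (Statistical Considerations) lists the outcomes: "Secondary outcome measures will include alcohol craving scales, alcohol withdrawal assessment using the CIWA, perceived stress scale", followed by a life-events scale and the COPE.

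The schedules are in Section V.3:

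- PSS (Stress-Related Assessments): "It will be used to assess stress levels weekly in study patients during treatment and at the follow-up appointment".
- AUQ (Substance Use measures): "The AUQ will be given weekly and at follow-up interviews". A second entry, under Abstinence Measures, says "This self-report will be completed weekly throughout the study".
- CIWA (Abstinence Measures): "The assessment will be administered weekly and at followup interviews".

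Section VI.A.3 gives another frequency: "Alcohol craving, abstinence symptoms, mood and perceived stress scale and side effects will be assessed twice weekly".

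Other instruments have an explicit pre-dose time point. The ASI is given before treatment, the Substance Use Calendar covers the 90 days before treatment, and for the COPE the text reads "In this study we will assess stress-related coping at baseline and once during treatment and at the follow-up".

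On analysis, Section V.12 assigns CIWA and perceived stress scores to non-parametric tests over the treatment phase and names no baseline term. Its Data Analytic Procedures prescribe mixed models for the aims, without listing a pre-dose score among the fixed effects. They enter a covariate only where a comparison of the arms at the outset shows a difference.

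**The concern.** Craving, stress and withdrawal differ between people in ways that persist over weeks. A score taken before the first capsule removes part of that variation from the arm comparison. Without it, the variation stays in the error term with only 30 participants per arm, and a chance imbalance on these scales can be neither seen nor adjusted for. The craving ratings labelled baseline in the laboratory schedule (Table 1) do not fill the gap, because the sessions take place in week 2 of study medication.

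This matters for the study's own purpose. Section V.12 says the findings will be used to estimate effect sizes for a larger trial, so the precision of these estimates counts even though the study is preliminary. A pre-dose score also cannot be recovered once dosing has begun.

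**Working it through.** **Is there a figure to reproduce?** No. The documents give no significance level, power, standard deviation or sample-size derivation for these scales.

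**Inputs.** The documents give 30 per arm (Section V.3, Study Design and Overview: "vs placebo (PLA) treatment (N=30/group) over 8 weeks"). My assumptions are two-sided 5% significance, 80% power, one dose against placebo, a normal approximation, and a correlation r between scores that is varied over a range.

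**Unadjusted, single score.** Detectable difference = (1.960 + 0.842) × √(2/30) = 0.72 SD.

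**Adjusted, single score.** The variance is multiplied by 1 − r². For r = 0.3, 0.5 and 0.7 the factors are 0.91, 0.75 and 0.51, so the variance falls by 9%, 25% and 49%. The detectable difference becomes 0.69, 0.63 and 0.52 SD.

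**Mean of 8 weekly scores, equal correlation r.** In units of the variance of one score, the variance is (1 + 7r)/8 without the pre-dose score and (1 + 7r)/8 − r² with it. The equivalent n per arm is 30 divided by the ratio of the two. Detectable differences are in SD of a single score.

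| r | Without | With | Ratio | Variance cut | Equivalent n per arm | Detectable difference |
|---|---|---|---|---|---|---|
| 0.3 | 0.3875 | 0.2975 | 0.768 | 23% | 39 | 0.450 to 0.395 |
| 0.5 | 0.5625 | 0.3125 | 0.556 | 44% | 54 | 0.543 to 0.404 |
| 0.7 | 0.7375 | 0.2475 | 0.336 | 66% | 89 | 0.621 to 0.360 |

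**Decaying (AR(1)) correlation.** Here scores k weeks apart correlate as ρ to the power k, so a pre-dose score says less about later weeks. With c the correlation between the pre-dose score and the 8-week mean, the ratio for the mean is 1 − c². For week 8 alone it is 1 − ρ¹⁶.

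| ρ | c | Ratio, 8-week mean | Variance cut, mean | Variance cut, week 8 |
|---|---|---|---|---|
| 0.6 | 0.297 | 0.912 | 9% | 0% |
| 0.7 | 0.397 | 0.842 | 16% | 0% |
| 0.8 | 0.535 | 0.714 | 29% | 3% |
| 0.9 | 0.729 | 0.469 | 53% | 19% |

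**Twice-weekly scores.** If the Section VI.A.3 frequency applied, 16 scores would replace 8. Under equal correlation of 0.5 the variance would be (1 + 15 × 0.5)/16 = 0.531 without and 0.281 with the pre-dose score, a cut of 47% instead of 44%. The frequency conflict therefore changes this result little.

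**Related figure in the documents.** Section V.3 (Laboratory Assessments) gives a test-retest reliability of 0.84 for the AUQ, without the retest interval. It is best read as an upper bound over eight weeks. No such figure is given for the PSS or CIWA.

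**The case against.** A reader might infer that these scales are given only on treatment and at follow-up, so that no pre-dose value exists. The documents do not support that.

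- Only the PSS entry is tied to the treatment period. The AUQ and CIWA entries are simply weekly, and one AUQ entry spans the whole study.
- Section V.3 places unnamed psychological assessments before enrollment and requires intake assessments to be complete before randomization.
- Silence about baseline is weak evidence here. Section V.12 cites anxiety symptoms among the measures for comparing the arms at baseline, yet the HADS is listed only among weekly measures.

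A reader might also infer that the first weekly score is always on drug, because the full assigned dose starts at once. The text does not say whether the first weekly battery precedes the first capsule, and the CANTAB baseline is set in the first week of enrollment.

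It can further be said that the study is mostly descriptive, that randomization protects the comparison, that alcohol use (a primary outcome) and the COPE do have baselines, and that the calculation models an adjusted analysis that is not planned. All of this stands and limits the size of the point. It does not remove it: nothing in the text secures a pre-dose score on these three scales, and the analysis rules make no dependable use of one.

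**Conclusion.** The point holds as a gap in specification together with a gap in the analysis plan. A pre-dose AUQ, CIWA or PSS is not specified. Collecting one would not be enough, because the non-parametric comparisons name no baseline term and the covariate rule depends on an observed imbalance.

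The consequence is lost precision and a missing balance check on some secondary scales. A reader might infer that the arm comparisons are biased, but with random assignment they are not. Nor do the documents show that the loss must be large. For the 8-week mean, adjustment would save 23–66% of the variance under equal correlation of 0.3–0.7 and 9–53% under decaying correlation with lag-1 values of 0.6–0.9. For week 8 alone under decay it would save 0–19%. All of these rest on assumed correlations and on an adjusted analysis of means. This is a cheap improvement, not a flaw that undermines the trial.

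**What to change.** 1. State in Section V.3 that the AUQ, CIWA and PSS are each given once at intake, after consent and before the first dose. If this already happens, write it down.
2. In Section V.12, replace the imbalance-triggered covariate rule for these scales. Enter the pre-dose score of each scale as a fixed covariate in its arm comparison, whether or not the arms differ on it. Use a repeated-measures model of the on-treatment scores, or a rank-based analysis of covariance if the distributions require it.
3. Reconcile the weekly schedule in Section V.3 with the twice-weekly one in Section VI.A.3, so that the set of scores entering the model is defined.

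The cost is one administration of 8 + 13 + 14 = 35 items, a few minutes of participant time at a visit that already takes place, and a short change to the analysis text.
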